DASH	Disabilities of the Arm, Shoulder and Hand
EQ-5D-5L	EuroQol-5 dimension-5 levels
ITT	Intention-to-treat
PROM	Patient reported outcome measures
REC	Research ethics committee
ROM	Range of movement
SAE	Serious adverse event
VAS	Visual analog scale
YTU	York Trials Unit

2. Definition of terms/acronyms

3. Design

SOFFT is a large pragmatic, two-arm, parallel group, individually randomised, multi-centre, noninferiority, controlled trial. The two arms are: standard tension band wiring (control); tension suture repair (intervention). There will be a 9-month internal pilot to assess assumptions about recruitment and fidelity of implementation of the tension suture technique.

This document has been written based on information contained in the study protocol, in which full details of the background and design of the trial are presented [1].

4. Trial Objectives

4.1 Primary objective

The primary aim of this study is to determine whether tension suture repair is not inferior to traditional tension band wiring for the internal surgical fixation of Mayo Grade IIA fractures of the olecranon in adult patients (\geq 16 years old).

4.2 Secondary objectives

Secondary aims are to:

- Undertake a 9-month internal pilot to obtain robust estimates of recruitment and confirm trial feasibility.
- Assess the rate of re-operation and other secondary outcomes, including patient satisfaction, pain, radiological union, range of elbow movement, and the occurrence of complications.
- Investigate the cost-effectiveness of the two interventions from the NHS perspective in order to identify the most efficient provision of future NHS care and to describe the resource impact on the NHS for the two treatment options (economic evaluation not detailed in this analysis plan, this will be written separately).

5. Follow-up

Following baseline, randomisation and treatment, all participants will be followed up for 18 months including a follow up visit at 4 months post-treatment, then questionnaires to be completed by the participant at 12 months and 18 months post-randomisation. Those patients that reach 24 months within the planned follow-up period will be asked to complete an additional questionnaire at 24 months.

In the event of local restrictions arising from COVID-19, the 4-month visit may be conducted remotely via telephone or video call.

6. Outcomes

6.1 Primary outcome

The primary outcome will be the Disabilities of the Arm Shoulder and Hand (DASH) score, at 4-months, the point at which the patient should have recovered from the initial intervention and bony union should be complete [2].

Fracture of the olecranon affects the ability to bend and straighten the arm as well as to turn the hand up and down, thereby affecting a range of everyday activities. The DASH has been chosen as the primary outcome measure because it captures the range of ways in which patients are likely to be affected by the fracture including activities of daily living, pain, social activities and sleep (http://www.dash.iwh.on.ca/). The 30-item PROM was designed for use in people with musculoskeletal disorders of the upper limb and is a reliable and valid instrument [3].

Baseline assessment will be completed prior to randomisation and will ask participants about their functioning in the week before their injury and their functioning since their injury (but prior to their surgery).

6.2 Secondary outcomes

Secondary outcomes will be collected at 4, 12 and 18 months post-randomisation for all participants, and at 24 months post-randomisation only for those who reach that follow-up point within the trial recruitment and follow-up window of up to month 48 of the study. These time points will enable identification of early complications and later re-operations and gather data to inform resource use and work impact. The following secondary outcomes will be assessed:

• **DASH** score (at 12, 18, and 24 months) [3]

- **Pain using a visual analog scale (VAS)**: A continuous scale, the scale is anchored by "no pain" (score of 0) and "worst imaginable pain" (score of 100), using a 100-mm scale, measuring average pain over the past week [4].
- Net Promotor Score (Patient Satisfaction): This assesses the likelihood of the patient recommending the healthcare received to friends or relatives using an 11-point numeric scale with 0 representing 'not at all likely' and 10 representing 'extremely likely' [5].
- **EuroQol 5 Dimensions (5L) Score (EQ5D-5L)**: Measures health-related quality of life in terms of 5 dimensions: mobility, ability to self-care, ability to undertake usual activities, pain and discomfort, anxiety and depression. The EQ-5D-5L will be scored according to the user guide [6]. This will be assessed as part of the health economic analysis.
- **Radiological union**: Union will be defined as the presence of bridging trabeculae seen on anterior-posterior and lateral x-rays of the elbow at 4 months. The assessment of union will be undertaken by assessors independent of the trial.
- **Complications**: Information on all complications will be collected. Expected complications that will be recorded will include (but not be limited to) deep wound infection, superficial infection, rehospitalisation, nerve and skin problems. Intra-operative complications and post-operative complications (at 4, 12, 18 and 24 months) will be collected and reported.
- Elbow range of movement (ROM): Elbow range of flexion, extension, pronation and supination will be assessed at 4 months by a suitably trained independent observer using a hand-held goniometer following trial specific instructions (this assessment will not be performed where local COVID-19 restrictions require the 4 month visit to be conducted remotely).
- **ROM (participant reported)**: Participants will be asked to obtain photographs of full elbow flexion and extension at 4 months following trial specific instructions. Images will be transferred to YTU and sponsor in order for measurement of ROM to be undertaken by a central reviewer using the procedure described by Meislin et al. [7]. Two independent assessors will perform each measurement three times, an average will be calculated across all measurements (3x measurements per 2x assessors = 6 measurements in total).
- **Re-operations related to the injury or to remove the fixation material**: Data will be collected on the reasons for re-operation e.g. discomfort, stiffness, prominent fixation device, infection, patient choice, surgeon choice.
- **Resource use and work impact**: Costs associated with each type of surgery and related complications, hospital stays, primary care consultations, work impact of both interventions will be collected (economic evaluation will be given in a separate analysis plan).

Scoring of instruments

DASH

Participants will be asked at baseline (pre and post injury) and at 4, 12, 18 and 24-months (for those reaching 24-months within the follow-up period) post-randomisation to complete the DASH questionnaire. The DASH questionnaire comprises of 30 questions measuring symptoms and function. All items are scored on a 5-point scale from 1 (no difficulty/symptoms) to 5 (extreme difficulty/symptoms). The arithmetic mean of at least 27 of the 30 items is transformed by (mean - 1)*25 into the scale from 0 = no symptoms/full function to 100 = maximal symptoms/no function for the DASH total score [3]. At least 27 out of the 30 items must be completed for a score to be calculated, if less than 27 items are completed then a score will not be calculated. If more than one box per item is selected and the boxes are adjacent, then the worst case will be selected, otherwise the item will be treated as missing.

6.3 Other collected variables

In addition to the primary and secondary outcomes the following information will also be collected during the trial:

- date of birth
- sex
- ethnicity
- co-morbidities (cardiovascular disease, respiratory disease, diabetes mellitus, other endocrine diseases, renal disease, neurological, musculoskeletal, cancer, other illnesses)
- COVID-19 status on admission to surgery
- fracture details (which elbow is injured, is it the dominant arm, how the injury occurred)
- fracture history (previous fractures or previous surgery to injured elbow)
- concomitant injuries
- living arrangements
- smoking status and smoking history
- alcohol consumption
- current medications
- qualifications
- working status
- treatment preference (for consenting and non-consenting patients)

The change of status CRF will be used to record any changes in participant status within the study including the patient withdrawing from treatment; the patient no longer attending hospital visits but agreeing to complete postal questionnaires; the patient no longer completing trial postal questionnaires but agreeing to allow research staff to collect data from medical records; the patient no longer wishing to complete any follow-up questionnaires; the patient withdrawing from all aspects of the trial; patient death (in the event of death a SAE form will also be completed).

7. Data

7.1 Case Report Forms

Participants are posted a paper case report form (CRF) questionnaire at 12, 18 and 24 months (for those that reach 24-month time point) post-randomisation. Completed questionnaires will be returned to YTU to be scanned and processed by YTU data management. The 4 month visit will be conducted in clinic, but may be conducted remotely in the event of local restrictions arising from COVID-19. Participants will be asked to indicate the method of collection by ticking the relevant box (in person, by telephone, other) on the front of the CRF.

The data collected by sites using paper CRFs, will be mailed to YTU to be entered/scanned into a secure web-based interface. When necessary, a site can securely return the CRF electronically. Data collected via telephone or video call will be collected onto paper CRFs or entered directly into a spreadsheet.

A copy of the CRFs with the variable names from the database (known as 'specs') will be kept by the Trial Statistician in the Statistical Master File.

7.2 Electronic/non-paper data

Anonymised intra-operative photographs taken by the clinical team will be securely transferred to YTU by email or other agreed secure NHS electronic imaging transfer method.

Anonymised photographs taken by participants to assess ROM will be transferred to YTU by email or printed copies posted. Measurements from the photographs will performed by independent physiotherapists based on the Meislin et al., (2015) paper. Measurements will be entered directly into an excel spreadsheet and provided for analysis. The following information will be provided: Patient ID,

Date sent to physiotherapists, Date of physiotherapist review/measurement, Initials of physiotherapist, Image quality level, Measurement 1 - Left arm flexion (degrees), Measurement 2 - Left arm extension (degrees), Measurement 3 - Right arm flexion (degrees), Measurement 4 - Right arm extension (degrees).

7.3 External datasets

No external datasets are required for this study.

7.4 Management database

All participant-reported data is identified solely by the unique participant trial ID. No other identifying details will be printed or input onto these documents. These CRFs are returned by post or electronically to YTU where they are scanned, using Teleform data capture software, into a bespoke data management system. This system is separate from the trial management system and contains no identifying details. All data are error checked and validated to ensure accuracy according to procedures detailed in the trial Data Management Plan. The paper CRFs are held securely in a controlled access area in locked cabinets but separate from the consent forms.

Both the trial management system and the data management systems are held on secure University of York servers with access limited to specified members of YTU staff as detailed in the delegation log.

8. Sample Size

There will be a 24-month recruitment period for the SOFFT trial. The total target sample size will be 280 participants. This was calculated using the standard deviation values for the DASH which range from 16 to 28 depending on the population under study [2, 8-12]. To be conservative a SD of 23 was assumed. Minimal clinical important differences for the DASH are around 10 points from individual studies using anchor-based methods [3, 10]. We estimate that a 10 point difference on the DASH at 4 months represents the threshold at which differences become important, and which would represent an appropriate non-inferiority margin. For 90% statistical power, 224 participants are required to establish non-inferiority of suture fixation compared with tension band wiring technique within a margin of 10 points on the DASH (SD=23), based on the upper limit of a 95% two-sided confidence interval (equivalent to a one-sided 97.5% confidence interval). Assuming 20% attrition at 4 months follow-up, gives the total target sample size 280.

9. Randomisation and blinding

Randomisation will be undertaken by York Trials Unit (YTU). When patients have given written informed consent and all the baseline forms have been completed, the authorised site research staff will contact YTU either by accessing a secure, internet-based randomisation service website hosted by York Trials Unit (https://ytu.york.ac.uk/YorkRand/) to obtain the patient's treatment allocation and enrol the patient into the study. Research staff will be required to provide the patient's trial identification number and other details to confirm patient eligibility in order to avoid inappropriate entry of patients into the trial. Participants will be randomly allocated in a 1:1 ratio to either tension suture repair or tension band wiring, using computer generated permuted blocks of random sizes, stratified by centre.

The Statistician will not be blinded to group allocation, nor will other members of the study team who are actively involved in the administration of the study. Participants will not be informed of which treatment they have received and the surgical wound is the same. However, if the wire protrudes or becomes uncomfortable, or the participant has sight of the x-ray, it may become apparent to the participant which intervention they have received. The investigator will record on the 4-month follow-up CRF whether they are aware of any inadvertent un-blinding of the participant (without asking the participant).

10. Analysis of internal pilot phase

There will be a 9-month internal pilot phase to assess assumptions about recruitment and the fidelity of implementing the tension suture repair technique.

The recruitment rate (defined as the proportion of eligible patients recruited) and 95% confidence interval (CI) will be estimated from the data collected up to the end of the pilot phase.

A CONSORT diagram will be produced to show the flow of participants through the study and the following outcomes calculated: number of eligible patients; proportion of eligible patients approached for consent; proportion of eligible patients not approached and reasons why; proportion of patients approached who provide consent; proportion of patients approached who do not provide consent; proportion of patients providing consent who are randomised; proportion of patients randomised who do not receive the randomly allocated treatment; proportion of patients dropping out between randomisation and follow-up.

Data will be summarised on the reasons why eligible patients were not approached, reasons for patients declining to participate in the study; reasons why randomised patients did not receive their allocated treatment and reasons for drop-out, if available.

Results will be compared against the study's recruitment assumptions and progression targets, and continuation of the trial or relevant modifications will be decided by the funding body.

Any deviations from technique recorded on the Surgery Fidelity Checklist CRF will be reported, with reasons where provided.

11. Final analysis

11.1 Analysis software

All analyses will be conducted in Stata v17 (StataCorp, [name]), or later (to be confirmed in final report).

11.2 Analysis principles and populations

Analyses will follow the principles of intention-to-treat (ITT) with participant's outcomes analysed according to their original, randomised group, where data are available, irrespective of deviations based on non-compliance. One-sided 97.5% confidence limits (equivalent to the upper bound of the two-sided 95% confidence interval) will be reported for the primary outcome and secondary analysis of DASH scores. There will be no pre-defined non-inferiority margins for the remaining secondary outcomes, these will be compared for evidence of superiority and two-sided tests at the 5% significance level will be used.

11.3 Screening, eligibility, recruitment and follow-up data

Recruitment graphs presenting the overall recruitment by month, and the actual vs target recruitment will be produced.

The flow of participants through the trial will be presented in a CONSORT diagram (see Appendices).

Follow-up response rates to the participant questionnaires (including time to response) will be summarised overall and by treatment group.

The number, type and timing of withdrawals will be presented overall and by treatment group, with reasons where provided.

The type of consent provided (remote or in clinic) and the method of follow-up at 4-months (in-person, telephone interview, other) will be reported as frequencies and percentages.

11.4 Baseline data

Participant baseline data will be summarised descriptively by trial arm and presented in tabular form (as randomised and as analysed). No formal statistical comparisons will be undertaken. Continuous measures will be reported as means and standard deviations (and/or median, interquartile range, and minimum and maximum as appropriate) and categorical data (e.g., data on further procedures and complications) will be reported as frequencies and percentages. Example tables are provided in the appendix (Section 15.2.1).

11.5 Primary analysis

DASH scores will be analysed using a mixed-effects regression model, with DASH scores at 4, 12 and 18-months follow-up as the dependent variable, adjusting for baseline DASH scores (pre-injury), age at randomisation (continuous), prescribed NSAIDs (binary; prescribed NSAIDs or not prescribed NSAID), previous elbow fractures (binary; previous elbow fracture or no previous elbow fracture), diabetes status (binary; diabetic or non-diabetic), smoking status (binary; current regular smoker or not a current regular smoker), drinks alcohol (binary; drinks alcohol or does not drink alcohol), randomised treatment group, time, and treatment group-by-time interaction as fixed effects and including treating centre and participant as random effects.

The DASH measure will be taken twice at baseline; pre and post-injury. We have outlined that the preinjury measure will be used in the primary analysis model as pre-injury function is more relevant. The post-injury scores will be examined for balance and if there is an imbalance across arms this will also be added to our primary analysis model.

The correlation of observations within participants over time will be modelled using participant as a random effect. The Akaike information criterion (AIC) will be used to compare models specifying different correlation structures (smaller values preferred), the most appropriate pattern will be used for the final model. All model assumptions will be checked, and if they are in doubt transformations of the outcome data will be considered. The estimated treatment group differences at 4 months will be reported as the primary endpoint with its associated one-sided 97.5% confidence interval. Example tables are provided in the appendix (Section 15.2.2).

Non-inferiority will be accepted if the upper bound of the one-sided 97.5% confidence interval (equivalent to the upper two-sided 95% confidence limit) for the treatment difference at 4 months lies below the non-inferiority margin of 10 points. Further details on this decision can be found in appendix 15.1.

Primary analysis will be checked by a second statistician on completion, this will be documented using *F16: Primary Analysis Sign Off* Form.

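### Post-injury DASH enters the primary non-inferiority model only if the arms look imbalanced, with no criterion, so the primary model is not fixed in advance and precision is lost when the arms are judged balanced

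*SAP*

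**What the plan says.** SAP section 6.1 has participants report DASH twice at baseline, once for the week before injury and once for "their functioning since their injury (but prior to their surgery"). Both come before allocation: "Baseline assessment will be completed prior to randomisation".

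Section 11.5 treats the two scores differently. The pre-injury "measure will be used in the primary analysis model as pre-injury function is more relevant". The post-injury score is conditional: "if there is an imbalance across arms this will also be added to our primary analysis model". The section does not say how imbalance is measured, how large it must be, who decides, or whether the decision precedes sight of outcome data.

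Two other sections bear on this. Section 11.4 says of baseline data: "No formal statistical comparisons will be undertaken". Section 9 says: "The Statistician will not be blinded to group allocation".

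The decision rule in section 11.5 is that the upper one-sided 97.5% limit "for the treatment difference at 4 months lies below the non-inferiority margin of 10 points". Nothing in the SAP commits to reporting the model both with and without the post-injury score.

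**The concern.** The sentence leaves two possible primary models. Two statisticians could follow the SAP on the same data, judge balance differently, fit different models and both be compliant. In a non-inferiority trial decided by one confidence limit against one margin, that choice can decide the conclusion.

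Chance imbalance is also a poor reason to adjust. Under proper randomisation any difference in a pre-randomisation score arises by chance. What makes a covariate worth including is how well it predicts the outcome, and that can be judged before the data are seen. Adjusting only after an apparent imbalance gives up the precision that the covariate would bring in every other case.

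**Working it through.** **Inputs from the SAP (sections 8 and 11.5).** Margin 10, SD 23, one-sided alpha 0.025, power 90%, 1:1 allocation, 20% attrition.

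**The plan's own figure.** n per arm = 2 × SD² × (1.960 + 1.282)² / margin² = 2 × 529 × 10.507 / 100 = 111.2, rounded up to 112. The total is 224, and 224 / 0.80 = 280. Both stated figures reproduce.

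**Assumption not in the SAP.** The correlation r between post-injury DASH and 4-month DASH. It is varied from 0 to 0.5.

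**How often chance looks like imbalance.** With 112 per arm the standardised difference has standard error √(2/112) = 0.134. It exceeds 0.1 in about 45% of trials and 0.2 in about 14%. Whether the covariate enters therefore depends heavily on the unstated cut-off.

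**How far the estimate can move.** An imbalance of 0.2 SD shifts the 4-month estimate by 0.2 × r × 23:
- r = 0.1: 0.46 points
- r = 0.3: 1.38 points
- r = 0.5: 2.30 points

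**Precision available.** Adjustment multiplies the standard error by √(1 − r²), which is 0.980, 0.954 and 0.866 for r = 0.2, 0.3 and 0.5. These are reductions of about 2%, 5% and 13%.

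**Simulated operating characteristics.** Settings: 112 per arm, SD 23, a single 4-month outcome, and linear regression with and without the covariate. Type I error is taken at a true difference of 10 and power at 0. In the rule columns the covariate enters when the standardised difference exceeds a fixed cut-off between 0.1 and 0.25.

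| r | Type I error, rule | Type I error, more favourable model chosen | Power, rule | Power, always adjust |
|---|---|---|---|---|
| 0.2 | 2.4–2.5% | 3.0% | 90.2–90.7% | 91.0% |
| 0.3 | 2.3–2.4% | 3.3% | 90.6–91.6% | 92.5% |
| 0.5 | 1.9–2.2% | 3.6–3.7% | 91.3–94.2% | 96.3% |

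Always adjusting keeps type I error at about 2.5% throughout. The fixed rule is slightly conservative. When imbalance is small, the unadjusted estimate varies less than its standard error implies, and when imbalance is large, the adjustment corrects for it.

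**How often the two models disagree.** With a true difference of 0, they give opposite non-inferiority verdicts in about 4.3% of trials at r = 0.3 and 7.4% at r = 0.5. With a true difference equal to the margin, the figures are about 1.5% and 2.3%.

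**The case against.** A reader might infer that the clause inflates the type I error of the primary test. The SAP does not support that. Entry depends on the balance of a pre-randomisation variable, not on the outcome or the treatment estimate, and such a rule applied mechanically is slightly conservative. The 3.0–3.7% figures describe an analyst who sees both results and keeps the better one. The SAP proposes nothing of the kind. What stands is that the open wording and the unblinded statistician do not exclude it, and that the second statistician's check in section 11.5 comes on completion, too late to fix the choice in advance.

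A reader might also say that the score is discarded. That is too strong. It is tabulated by arm in template Table 2 and enters the model if imbalance is seen, and pre-injury DASH is always adjusted for. The absence of baseline testing in section 11.4 is sound practice in itself. It matters here only because it leaves no test to supply the missing criterion.

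The gain from adjustment is uncertain. The primary model already contains pre-injury DASH, age and five other covariates and uses repeated measures, so the relevant quantity is the partial correlation given those. It is unknown and could be small. At r = 0.2 the power gain is under 1 percentage point.

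The sponsor's reason, that pre-injury function is more relevant, could justify never including the post-injury score. It cannot justify including it only when chance produces a difference. A fixed decision to exclude would also close the model in advance. Inclusion is preferred because it is valid at any correlation and costs almost nothing.

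**Conclusion.** The point holds as a defect of pre-specification and efficiency. The covariate set of the primary non-inferiority model is left to a judgement without a criterion, made by a statistician who knows the allocation. Compared with always adjusting, a mechanically applied rule costs about 1 to 2 percentage points of power at an assumed correlation of 0.3 (92.5 − 91.6 = 0.9; 92.5 − 90.6 = 1.9). At 0.5 it costs about 2 to 5 points (96.3 − 94.2 = 2.1; 96.3 − 91.3 = 5.0).

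Type I error is not inflated unless results influence the choice, so an inflated error rate is a possibility left open and not a property of the plan. The sample size is not in question.

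The absence of a criterion is certain from the text. The sizes rest on the assumed correlation and on a single-time-point regression without the other covariates or the centre effect. The change should be made, but the point does not undermine the trial.

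**What to change.** 1. Delete the conditional sentence in section 11.5.
2. Include post-injury DASH alongside pre-injury DASH as a fixed covariate in the primary model, regardless of balance.
3. Add a simple rule for missing baseline scores, for example mean imputation or a missing indicator. Section 11.6 admits to the primary model only participants with complete baseline data, a DASH score needs at least 27 of 30 items, and the SAP has no baseline imputation rule. Without one, always including the score could drop participants.
4. Use the same covariates in the analyses that reuse the primary model: CACE, the age subgroup analysis and the 24-month DASH model.
5. Report the model without post-injury DASH as a sensitivity analysis.

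The cost is SAP wording, one degree of freedom and one baseline imputation rule. The 224 evaluable and 280 randomised participants remain sufficient: with the adjusted SD of 23 × √(1 − r²), the number needed for 90% power is 224, 222, 204 and 168 for r = 0, 0.1, 0.3 and 0.5.
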